3.2 Exclusion criteria

Patients eligible must not meet **any** of the following criteria:

1. Patients with known hypersensitivity to any of the excipients of abemaciclib
2. History of carcinomatous meningitis
3. Prior therapy with abemaciclib.
4. The patient has serious and/or uncontrolled preexisting medical condition(s) that, in the judgment of the investigator, would preclude participation in this study (for example, interstitial lung disease, severe dyspnea at rest or requiring oxygen therapy, severe renal impairment [e.g. estimated creatinine clearance <30ml/min], history of major surgical resection involving the stomach or small bowel, or preexisting Crohn's disease or ulcerative colitis or a preexisting chronic condition resulting in baseline Grade 2 or higher diarrhea).
5. Females who are pregnant or lactating.
6. The patient has active systemic bacterial infection (requiring intravenous [IV] antibiotics at time of initiating study treatment), fungal infection, or detectable viral infection (such as known human immunodeficiency virus positivity or with known active hepatitis B or C [for example, hepatitis B surface antigen positive]. Screening is not required for enrollment.
7. The patient has a personal history of any of the following conditions: syncope of cardiovascular etiology, ventricular arrhythmia of pathological origin (including, but not limited to, ventricular tachycardia and ventricular fibrillation), or sudden cardiac arrest.
8. Presence or history of a malignant disease other than thyroid cancer that has been diagnosed and/or required therapy within the past year and is undergoing active anticancer treatment. Exceptions to this exclusion include the following: completely resected basal cell and squamous cell skin cancers, and completely resected carcinoma in situ of any type.

3.3 Informed Consent Process

All participants must be provided a consent form describing the study with sufficient information for participants to make an informed decision regarding their participation. Participants must sign the IRB approved informed consent prior to participation in any study specific procedure. The participant must receive a copy of the signed and dated consent document. The original signed copy of the consent document must be retained in the medical record or research file. A high definition electronic copy such as PDF scan or electronic photograph of entire signed consent form is acceptable for documentation of consent.

3.4 Registration Process

The sites will register the subject on OnCore within 5 business days and immediately notify the Stanford Study Coordinators, Monday through Friday, between 9:00 a.m. and 5:00 p.m. (Pacific Time). The individual notifying the Stanford study team will also provide the subject's eligibility information when eligibility checklist is complete, with the secondary reviewer to be signed off by a designated Stanford Research Staff member. No subject may begin study treatment until registration, eligibility confirmation, and assignment of a subject identification number is completed.

At registration, Stanford will sequentially assign eligible subjects an identification number. As confirmation, Stanford will provide the Investigator with written verification of the subject's registration by e-mail or fax. The subject's identification number will be used on all subject-specific Case Report Forms (CRFs) and serious adverse event (SAE) forms. Participant information should be entered into Oncore® within 5 business days.

3.5 Randomization Procedures

There is no randomization.

3.6 Study Timeline

Primary Completion:

The study will reach primary completion 24 months from the time the study opens to accrual.

Study Completion:

The study will reach study completion 36 months from the time the study opens to accrual.

Definition of end of the Study

The arm will be completed when 17 patients have evidence of disease progression by RECIST, unacceptable toxicity, withdrawal of consent, or discontinuation of the trial for any other reason. Patients who have RECIST-defined PD as assessed by the investigator but who, in the opinion of the investigator, have evidence of continued clinical benefit from study drug may continue to receive the study medication. In such cases, these patients must continue to be followed for safety and efficacy assessments as per the schedule of assessments.

At the completion or discontinuation of study medication, all patients will be seen within 30 days for an end of therapy evaluation. This will include a safety assessment for AE's SAE's. Any unused medication will be destroyed

4. TREATMENT PLAN

For this study, the term “treatment” refers to abemaciclib. The dose and schedule are listed under table 4-1.

Each cycle of therapy will be 28 days long. A completed cycle will be twice daily abemaciclib. Day 1 will be the first day that abemaciclib is taken, and the last day of a completed treatment cycle will be day 28. All doses prescribed to and taken by patients, any dose adjustments and interruption or discontinuations will be recorded in the clinical trial record.

Table 4-1 Dose and treatment schedule

Study treatments	Pharmaceutical form and route of administration	Dose	Frequency and/or Regimen
Abemaciclib	Tablet for oral intake	200 mg orally	Twice daily (28 day cycle)

Dosing regimen

Patients on the therapeutic portion of this trial will begin therapy on day 1 of Cycle 1 with the first administration of abemaciclib.

Administration of abemaciclib

The investigational pharmacist or designee will dispense abemaciclib to the patient at the beginning of each cycle. Patients will self-administer the doses of abemaciclib for the 28-day cycle.

- The institution will be supplied with abemaciclib by Lilly. Treatment will be administered orally daily at the doses noted on a continuous dosing schedule. The investigator must instruct the patient to take the treatment exactly as prescribed. Patients should take

treatment daily at approximately the same time each day, in the morning, afternoon, or evening.

- If vomiting occurs during the course of treatment, do not take another tablet before the next scheduled dose.
- Do not make up missed doses or partial doses (i.e., when the entire dose is not taken as instructed). A missed or partial dose will be defined as a case when the full dose is not taken within 8 hours after the approximate time of the usual daily dosing. That day's dose (or partial remaining dose) should be omitted, and continue treatment with the next scheduled dose on the following day.

Treatment duration

Patients will continue abemaciclib treatment until they experience any of the following:

- Disease progression determined by the local investigator.
- Unacceptable toxicity that precludes further treatment.
- Start of a new anti-cancer therapy.
- Pregnancy.
- Treatment is discontinued at the discretion of the investigator or patient.
- Lost to follow-up.
- Death.
- Completed.

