2.2 Study Agent/Device/Procedure

In the mammalian cell cycle, entry into S phase is achieved by CDK4/6. Abemaciclib is a small molecule inhibitor that is selective for CDK4 and 6. It blocks phosphorylation of the retinoblastoma tumor suppressor protein. This leads to impaired progression through the cell cycle and arrest in the G1 phase(Sledge, Toi et al. 2017). Currently, Abemaciclib is FDA-approved for use in breast cancer, with the package insert providing further information about pharmacology, dosage and administration, drug interactions and use in special populations:

https://www.accessdata.fda.gov/drugsatfda_docs/label/2017/208716s000lbl.pdf

For clinicaltrials.gov compliance

Abemaciclib is FDA approved for use in breast cancer. This clinical trial will not be seeking a new indication. An IND is not required in conjunction with this clinical trial.

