5. INVESTIGATIONAL AGENT/DEVICE/PROCEDURE INFORMATION

5.1 Investigational Agent/Device/Procedure

Abemaciclib is FDA approved and in regular use for clinical practice. For further details please refer to the abemaciclib investigator brochure.

For clinicaltrials.gov and Stanford Clinical Trials Directory compliance

Intervention Description

1. Abemaciclib 200 mg orally twice daily
2. Number of Cycles: until progression or unacceptable toxicity develops.

Arms/Groups

1. single arm study

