5.5 Study drug compliance and accountability

5.5.1 Study drug compliance

The patient will be asked to keep a diary of taking the medication, as well as bringing pill bottles to each clinic visit. At each visit, the patient's compliance in study medication according to protocol will be assessed by the investigator and/or study personnel. This information will be entered into the Drug Accountability Form and captured into the source document at each visit, in their medication diary.

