7.3 Guidelines for on-study patient management

7.3.1 Guidelines for Diarrhea Management

Clinical trial data indicates the majority of patients who receive abemaciclib will develop diarrhea. Our experience indicates early identification and intervention for the management of diarrhea has been helpful to patients.

At enrollment, patients should receive instructions on the prompt management of diarrhea. In the event of diarrhea, supportive care measures should be initiated as early as possible. These include the following:

- At the first sign of loose stools, the patient should initiate antidiarrheal therapy (e.g. loperamide) and notify the investigator for further instructions and appropriate follow-up.
- Patients should also be encouraged to drink fluids (e.g., 8 to 10 glasses of clear liquids per day).
- Site personnel should assess response within 24 hours.
- Refer to Table 7-1 for additional information for diarrhea management and dose modification.

Table 7-1: Dose Modification and Management- Diarrhea

At the first sign of loose stools, start treatment with antidiarrheal agents, such as loperamide.

CTCAE Grade	Abemaciclib Dose Modifications
Grade 1	No dose modification is required.
Grade 2	If toxicity does not resolve within 24 hours to \leq Grade 1, suspend dose until resolution. Dose reduction is not required.
Grade 2 that persists or recurs after resuming the same dose despite maximal supportive measures	Suspend dose until toxicity resolves to \leq Grade 1. Resume at next lower dose.
Grade 3 or 4 or requires hospitalization	

Dose level reductions should be made in 50 mg increments. For example, if the starting dose of abemaciclib is 200 mg twice daily, dose reduction 1 would be 150 mg twice daily, dose reduction 2 would be 100 mg twice daily.

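### The timing and missed-dose instructions in Section 4 use once-daily wording for a twice-daily drug, and the missed-dose sentence contradicts itself after a missed morning dose (minor)

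*Combined protocol and SAP*

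**What the plan says.** The prescribed schedule is consistent throughout the protocol. Table 4-1 in Section 4 gives 200 mg twice daily. Section 5.1 describes the intervention as "Abemaciclib 200 mg orally twice daily". The reduced levels in Section 7.3.1 keep the same frequency: "dose reduction 1 would be 150 mg twice daily, dose reduction 2 would be 100 mg twice daily". The CYP3A adjustments in Section 4.1 are also twice daily.

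The administration bullets in Section 4 are worded differently. Patients are to take "treatment daily at approximately the same time each day, in the morning, afternoon, or evening". A dose counts as missed or partial when the full dose "is not taken within 8 hours after the approximate time of the usual daily dosing". The dose for that day "should be omitted, and continue treatment with the next scheduled dose on the following day".

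Patients dose themselves at home. On compliance, Section 5.5.1 says: "The patient will be asked to keep a diary of taking the medication". Section 2.2 describes the drug as approved for breast cancer, "with the package insert providing further information about pharmacology, dosage and administration", but the insert is not among the documents.

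On a separate matter, Section 9.1.4.11 sets contraception for women of childbearing potential at 3 weeks after the last dose. Inclusion criterion 13 in Section 3.1, repeated in Appendix A, sets it at 3 months.

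**The concern.** Three features of the bullets assume a single daily intake: one time of day chosen from three, a lateness window counted from one usual daily time, and resumption the next day. Under a twice-daily schedule the last of these matters. A patient who misses the morning dose has another dose due that evening, and the sentence both points to it and passes over it.

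What is at stake is consistent dosing and a clear standard for compliance. Section 5.5.1 has compliance with the protocol assessed at every visit, Section 12.3 summarises it, and Section 4.2 allows removal for non-compliance. As the text stands, a patient who takes the evening dose departs from one half of the missed-dose sentence. A patient who skips it departs from the prescribed schedule. The protocol also provides for participating sub-sites, which could instruct patients differently.

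**Working it through.** The protocol states no figure for this point, so there is none to reproduce. The check compares the instructions and then counts doses.

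**Inputs**
- Dose and frequency: 200 mg twice daily (Table 4-1, Section 5.1).
- Cycle length: 28 days (Section 4).
- Reduced levels: 150 mg and 100 mg twice daily (Section 7.3.1).
- Response assessment: 8 weeks, plus or minus 4 (Section 10.1).
- Interval between the two daily doses: not given. I assume 12 hours and show 10 to 14.
- Rate of missed doses: not given, so the loss is stated per event.

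**Which dose comes next**

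| Dose missed | Next scheduled dose under Table 4-1 | Resuming the following day | Conflict |
|---|---|---|---|
| Morning | Same evening | Next morning | Yes; the evening dose is skipped |
| Evening | Next morning | Next morning | No |

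**Doses lost per missed morning dose**
- Planned per cycle: 2 x 28 = 56 doses; 56 x 200 = 11,200 mg.
- Resuming the following day: 2 doses lost, 400 mg, 2/56 = 3.6% of the cycle.
- Skipping only the missed dose: 1 dose lost, 200 mg, 1/56 = 1.8%.
- Excess: 1 dose, 200/11,200 = 1.8%. The share is the same at the reduced levels: 150/8,400 and 100/5,600 are both 1.8%.
- Over the 4, 8 and 12 weeks spanned by the response window: 1/56 = 1.8%, 1/112 = 0.9%, 1/168 = 0.6%.

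**Gap between doses after a missed morning dose**
- Resuming the following day: 12 + 24 = 36 hours from the previous evening's dose. If the overnight interval is 10 to 14 hours, the gap is 34 to 38 hours.
- Skipping only that dose: 24 hours, evening to evening.
- Missed evening dose: 24 hours, morning to morning, on either reading.

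**The 8-hour window**
- A dose taken at the limit falls 12 - 8 = 4 hours before the next one (2 to 6 hours for intervals of 10 to 14). The window closes before the next dose is due, so it can be applied per dose.

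**Contraception**
- 3 months is about 13 weeks, so the two periods differ by about 13 - 3 = 10 weeks.

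**The case against.** A reader might infer that the protocol plainly tells patients to cancel the evening dose. The documents do not support that. The same sentence refers to the next scheduled dose, which under Table 4-1 is the evening one. The neighbouring bullets require treatment to be taken exactly as prescribed, and the vomiting rule works per dose. The sentence is inconsistent with itself rather than a clear order to skip. This part of the objection stands, and it limits the point to a contradiction that needs removing.

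A reader might also take the 8-hour window as wrong for this schedule. It is shorter than the assumed intervals and can work, and nothing in the documents says that the resulting spacing is harmful. Its once-daily reference point needs rewording. Its length is for the sponsor to confirm.

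A third inference would be a weakened response result. The protocol gives no missed-dose rate and no link between a single skipped dose and response. Site staff instruct patients, doses are recorded, and diaries and pill bottles are checked at each visit, so any loss would be visible. The diary, the patient instructions and the package insert are not available, so whether any patient would in fact skip an evening dose cannot be known. What survives is narrower: none of these safeguards says which half of the sentence governs.

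On contraception, criterion 13 is a condition of entry, so every enrolled woman of childbearing potential has already agreed to 3 months. Section 9.1.4.11 does not waive that. It is an editorial mismatch, and it adds no weight to the dosing point.

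**Conclusion.** Minor, and wrong as written. The timing and missed-dose bullets do not fit the prescribed schedule, and after a missed morning dose the instruction contradicts itself. On the less favourable reading the cost is one extra dose per event, 1.8% of a cycle; after a missed evening dose it is nil. The dose count rests only on figures in the protocol. The gap of 36 rather than 24 hours rests on an assumed 12-hour interval.

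The two-stage rule in Sections 12.2 and 12.6.2, with its type I error and power, does not depend on this. The analysis sets in Section 12.4.1 need only one dose, so a skipped dose removes nobody from the analysis.

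**What to change.** Replace the timing and missed-dose bullets in Section 4 with wording per dose, for example:

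> Take one dose twice daily, at about the same two times every day. Never make up a missed or partial dose. Count a dose as missed if it has not been fully taken within 8 hours of its usual time (or within another window that the sponsor confirms). Skip only that dose, and take the next one at its usual time.

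This keeps a definition of a missed dose and removes the references to a single daily intake. As a separate correction, change 3 weeks to 3 months in Section 9.1.4.11.

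The cost is a few lines in an amendment, with the IRB approval that Section 11.2 requires. If the patient diary or dosing instructions repeat the present wording, they need the same change. There is no statistical cost.

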4.1 General Concomitant Medication and Supportive Care Guidelines

Abemaciclib is predominantly cleared by oxidative metabolism via CYP3A4. Clinical drug interaction studies with a CYP3A inhibitor and CYP3A inducer significantly altered the PK of abemaciclib and its circulating major metabolites.

CYP3A inducers

Avoid concomitant use of CYP3A inducers and consider alternative agents.

CYP3A inhibitors

Avoid concomitant use of strong CYP3A inhibitors (for example, voriconazole) and use caution with coadministered moderate (for example, ciprofloxacin) or weak (for

example, ranitidine) CYP3A inhibitors. If coadministration with a strong CYP3A inhibitor is unavoidable, reduce the abemaciclib dose to 100 mg twice daily or, in the case of ketoconazole, reduce the abemaciclib dose to 50 mg twice daily. In patients who have had a dose reduction to 100 mg twice daily due to adverse reactions, further reduce the abemaciclib dose to 50 mg twice daily. Avoid grapefruit or grapefruit juice. If a CYP3A inhibitor is discontinued, increase the abemaciclib dose (after 3-5 half-lives of the inhibitor) to the dose that was used before starting the inhibitor.

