6. DOSE MODIFICATIONS

Dose escalation guidelines

No doses escalation will be permitted on this study.

Dose modifications

For patients who do not tolerate the protocol-specified dosing schedule, dose adjustments are permitted in order to allow the patients to continue the abemaciclib treatment. Any changes in drug administration will be recorded in the clinical trial record.

For patients who do not tolerate the protocol-specified dosing schedule, adjustments are recommended in order to allow the patient to continue the study treatment. Refer to Section 7.3.1 for dose level reductions. For purposes of EDC entry, dose modification is defined as dose reductions and dose holds.

General guidelines for dose modifications

- For grade 1 and tolerable grade 2 treatment-related toxicities, with the exception of pneumonitis, patients may continue at the current dose of abemaciclib.
- For intolerable grade 2 treatment-related toxicities, with the exception of pneumonitis, dosing should be interrupted until resolution to grade 1 or lower followed by dose reduction to the next dose level.
- For grade 3 or grade 4 treatment-related toxicity, that is not considered by the investigator to be life-threatening, dosing should be interrupted and the patients should be followed until the toxicity resolution to grade 1 or lower. Following recovery from grade 3 or grade 4 events, study treatment may continue following a dose reduction to the next dose level, if, in the opinion of the Investigator, the patient continues to experience clinical benefit. For any grade 3 or grade 4 treatment-related toxicity that is considered by the investigator to be life-threatening, permanently discontinue study treatment.

All dose modifications, interruptions or discontinuations must be based on the worst preceding toxicity as graded by the NCI Clinical Toxicity Criteria version 5

Patients whose treatment is interrupted or permanently discontinued due to an AE must be followed until resolution or stabilization of the event. Patients requiring interruptions greater than 2 cycle (56 days) should be discontinued from abemaciclib treatment. All patients will be followed for safety until 30 days after the last dose of abemaciclib.

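### Section 4.1 makes the return to the pre-inhibitor dose mandatory when a CYP3A inhibitor is stopped, with no exception for a toxicity reduction made while the inhibitor was taken

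*Combined protocol and SAP*

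**What the plan says.** Section 4.1, under CYP3A inhibitors, advises against strong inhibitors. If one is unavoidable, the site is to "reduce the abemaciclib dose to 100 mg twice daily or, in the case of ketoconazole, reduce the abemaciclib dose to 50 mg twice daily". For patients already cut for toxicity before the inhibitor, it adds a rule for those with a "dose reduction to 100 mg twice daily due to adverse reactions, further reduce the abemaciclib dose to 50 mg twice daily". For weaker inhibitors it asks sites only to "use caution with coadministered moderate (for example, ciprofloxacin) or weak" agents, and sets no dose cut.

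The paragraph closes with the restoration rule. "If a CYP3A inhibitor is discontinued", the site must "increase the abemaciclib dose (after 3-5 half-lives of the inhibitor) to the dose that was used before starting the inhibitor".

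Section 6 opens with "No doses escalation will be permitted on this study". After a Grade 3 or 4 treatment-related event that is not life-threatening, and on recovery, "study treatment may continue following a dose reduction to the next dose level" if the investigator sees benefit. All modifications "must be based on the worst preceding toxicity". Section 7.3.1 fixes a dose level at 50 mg. Section 7.3.6 has the patient resume one level lower after a Grade 3 or 4 nonhematologic toxicity. Sections 6, 7.2 and 7.3 do not refer to 4.1, and 4.1 does not refer to them.

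**The concern.** A reduction for toxicity made before the inhibitor is safe under 4.1, because the pre-inhibitor dose already contains it. A reduction made while the inhibitor is being taken is not covered. The restoration rule is worded as an instruction, so a site that follows it raises the dose through the toxicity reduction as well as through the interaction adjustment.

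Section 6 does not settle the matter. Taken strictly, its ban on escalation forbids every increase that 4.1 orders. Taken as a ban on doses above 200 mg, it leaves the restoration untouched. It may well mean the second, but it does not say so.

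What is at stake is patient safety and consistency between sites. One investigator may return a patient to full dose after an event that called for a lower level, and another may hold the lower dose, each with a section of the protocol in support.

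**Working it through.** **Inputs**

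- Starting dose: 200 mg twice daily (Table 4-1, Section 5.1).
- Dose on a strong inhibitor: 100 mg; with ketoconazole, or if already at 100 mg for adverse reactions, 50 mg (Section 4.1).
- Moderate or weak inhibitor: no preset cut (Section 4.1).
- One toxicity level: 50 mg (Section 7.3.1).
- Dose after the inhibitor stops, read literally: the pre-inhibitor dose (Section 4.1).

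**Plan's own figures.** 200 − 50 = 150 and 150 − 50 = 100 reproduce reductions 1 and 2 in Section 7.3.1.

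**Formula.** With pre-inhibitor dose P and k toxicity levels taken on the inhibitor, the literal rule gives P. Keeping the toxicity reduction gives P − 50k. The difference is 50k mg per dose.

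**Dose paths (mg twice daily)**

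| Case | P | On inhibitor | After toxicity | Literal 4.1 | Reduction kept | Difference |
|---|---|---|---|---|---|---|
| Strong inhibitor, k = 1 | 200 | 100 | 50 | 200 | 150 | 50 |
| Strong inhibitor, earlier cut to 150, k = 1 | 150 | 100 | 50 | 150 | 100 | 50 |
| Ketoconazole | 200 | 50 | none (50 − 50 = 0) | – | – | – |
| Strong inhibitor, earlier cut to 100 | 100 | 50 | none (50 − 50 = 0) | – | – | – |
| Moderate or weak, k = 1 | 200 | 200 | 150 | 200 | 150 | 50 |
| Moderate or weak, k = 2 | 200 | 200 | 100 | 200 | 100 | 100 |

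In the first row the total rise is 200 − 50 = 150 mg per dose. Of this, 200 − 100 = 100 mg reverses the interaction adjustment and 50 mg reverses the toxicity level. The end doses compare as 200/150 = 1.33, or 2 × 50 = 100 mg per day. On a strong inhibitor no more than one level can be cancelled, since 100 − 2 × 50 = 0.

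**Comparison with toxicity first.** The path is 200, then 150 (toxicity), then 100 (strong inhibitor), then 150 when the inhibitor stops. Here 4.1 keeps the toxicity reduction without further wording.

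**One inferred step.** The ladder in Section 7.3.1 is given as an example and ends at 100 mg. A toxicity cut from 100 to 50 mg follows from the 50 mg step but is not listed. No minimum dose is stated, and 4.1 itself uses 50 mg. If 100 mg were the floor for toxicity cuts, the strong-inhibitor rows would drop out and only the moderate or weak rows would remain.

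**The case against.** The strongest reply is that full restoration may be right. Section 4.1 says CYP3A inhibition significantly alters abemaciclib's pharmacokinetics. A toxicity that appears on an inhibitor need not show intolerance of 200 mg taken alone, and 4.1 waits for the inhibitor to clear before the increase. This stands.

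It also limits two inferences a reader might draw. One is that the protocol treats identical patients differently because of the order of events. The two orders carry different evidence: in the inhibitor-first path, no toxicity had required a cut from 200 mg before the inhibitor began. The other is that 4.1 should impose a hard ceiling of 150 mg in the main example. The 100 mg step is fixed and need not match exposure exactly, so raised exposure may explain toxicity on a strong inhibitor too. The documents do not support a compulsory cap.

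The moderate or weak rows rest on a literal but strained reading. The restoration sentence names any CYP3A inhibitor, but it ends a paragraph whose only dose cuts are for strong ones, and it most naturally means undoing those. These rows are a reason to tidy the wording and add little weight.

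Other sections help in part. A site reading Sections 4.1, 6 and 7 together has toxicity language that favors the lower dose. However, Section 6 defines dose modification, for data entry, as reductions and holds, so its worst-toxicity line is supporting only. Adverse events are reviewed at every scheduled visit, and the investigator may reduce again or stop treatment. That limits harm after the increase but does not make the increase optional.

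Section 2.2 points to the package insert for dosage and interactions, and Section 5.1 to the investigator brochure. Neither is in the documents, so whether they cover this case is unknown.

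**Conclusion.** The point holds as a gap in a mandatory rule. Section 4.1 orders an increase that can cancel a toxicity reduction made under Sections 6 and 7.3, conflicts with the escalation ban in Section 6, and leaves the order of precedence unstated. It does not follow that returning to the pre-inhibitor dose is always wrong.

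On a strong inhibitor the size is one 50 mg level: 200 against 150 mg twice daily, or 150 against 100 mg for a patient already at 150 mg. This assumes that toxicity cuts may go down to 50 mg. On the literal reading for moderate or weak inhibitors, more than one level could be cancelled. No exposure ratio is claimed, because 4.1 is a step schedule.

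The number of patients affected is not stated. The strong-inhibitor path needs an unavoidable strong inhibitor, a qualifying toxicity, recovery, withdrawal of the inhibitor and continued treatment, so it probably concerns few of 17. Error rates, sample size and the response analysis are unchanged. This is a cheap improvement and a minor safety correction.

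**What to change.** In Section 4.1, state that stopping an inhibitor reverses only the interaction reduction by default. Then add that, where a toxicity reduction was made while on any CYP3A inhibitor, the dose may be increased at the investigator's judgment to no more than the pre-inhibitor dose. The toxicity reduction may instead be kept, at one 50 mg level below the pre-inhibitor dose for each reduction (200 − 50 = 150 mg in the main example).

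In Section 6, state that the restoration in 4.1 is the only permitted increase and never exceeds 200 mg twice daily.

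The cost is a few sentences, with no new visits, procedures or patients. The downside is that some patients whose toxicity came only from raised exposure may stay one level lower than they could tolerate.
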